If the blood sample cannot be obtained, the parent/guardian should be given the opportunity to bring the subject back to the study site for another attempt, as long as the subject continues to remain eligible for the study. All attempts should be made to obtain a blood sample; however, if the attempts are unsuccessful, the subject could continue in the study with all the study procedures including vaccination.

8) Inject the following study vaccines. Each vaccine should be administered in an assigned location (see Operating Guidelines) and documented appropriately:

Table 5.4: Vaccinations and route of administration at V05

Vaccine		Route of administration
SP0202 or Prevnar 13	Observer-blind but double-blind across SP0202	Inject IM into the anterolateral area of the thigh, preferably the right thigh
M-M-R_{II}	Open-label	Inject SC into the anterolateral area of the thigh (preferably the left thigh, ie, the opposite thigh from that used for SP0202 or Prevnar 13) or the outer aspect of the upper left arm
VARIVAX	Open-label	Inject SC into the anterolateral area of the thigh (preferably the left thigh, ie, the opposite thigh from that used for SP0202 or Prevnar 13) or the outer aspect of the upper right arm (ie, the opposite arm from that used for M-M-R _{II})

When multiple vaccines are administered at a single visit, each vaccine should be administered at a different anatomic site. If vaccines are given in the same limb, the injection sites should be separated by 1 inch / 2.5 cm or more, so that any local reactions can be differentiated ([40](#)).

Failure to administer vaccines in the designated limb will not constitute a protocol deviation, but should be recorded as a comment in the vaccination form of the eCRF.

- 9) Keep the subject under observation for 30 minutes and record any adverse reaction in the source document.
- 10) Give the parent / guardian a DC5. Remind parents to carefully report any clinical signs / diagnosis experienced at the same time as the fever episode $> 39.5^{\circ}\text{C} / 103.1^{\circ}\text{F}$.
- 11) Arrange an appointment for V06 (D330-420 + 14 days). Remind the parent / guardian to expect a telephone call 8 days after V05 and to bring back the DC5 when they return for V06 at a specified date and time.
- 12) Remind the parent / guardian to notify the site in case of a serious medical event occurs.
- 13) Complete the source document and the relevant CRFs for this visit.

Telephone Call 4 (8 [+2] days after Visit 5)

Note: If D8 falls on a weekend or a holiday, the telephone call may be made on the following business day.

- 1) Record relevant information concerning the subject's health status on the telephone contact form. If an SAE occurred, follow the instructions in [Section 10](#) for reporting it.
- 2) Remind the parent / guardian to do the following:
 - Complete the Day 0–7 pages of the DC5
 - Complete the remaining pages of the DC5, and bring them to V06
 - Notify the site in case of an SAE

Visit 6 (30 [+14] days after Visit 5): Collection of Safety Information and Blood Sample

- 1) If the DC5 information from Day 0–7 has not yet been obtained, obtain it at this time by interviewing the parents. Review the pages of the DC5 with the parent / guardian, including any AEs, medications, or therapy that occurred since vaccination.
- 2) Check medications and record reportable ongoing medications. Review temporary contraindications for blood sampling. Ensure the subject has not had any antibiotics within the previous 72 hours (3 days).
- 3) Conduct a physical examination and take subject's temperature if necessary, based on the health status of the subject.
- 4) Obtain the blood sample (BL0004 – 6 mL) (see [Section 7.1](#) for detailed instructions regarding the handling of blood samples).
- 5) Record the study termination.
- 6) Complete the source document and the relevant CRFs for this visit.
- 7) Complete the end of study CRF of the CRB.
- 8) Provide the memory aid (MA) to the subject's parent / guardian

Safety Follow-up Telephone Call (D 480 - 570 + 14 days)

The investigator or authorized designee will:

- 1) Ask the parent / guardian if the subject has experienced any SAE or AESI in the time since vaccination
- 2) Complete the relevant CRF for this phone contact.

A follow-up visit can be arranged depending on the information recorded during the phone call.

Follow-up of subjects with Related AEs or with AEs That Led to Study/Vaccination Discontinuation:

Unless a subject or subject's parent/guardian refuses further contact, each subject who experiences an AE (whether serious or non-serious) during the study must be followed until the condition resolves, becomes stable, or becomes chronic (even after the end of the subject's participation in the study) if *either* of the following is true:

- The AE is considered by the Investigator to be related to the product administered.
- The AE caused the discontinuation of the subject from the study or from vaccination.

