When multiple vaccines are administered at a single visit, each vaccine should be administered at a different anatomic site. If vaccines are given in the same limb, the injection sites should be separated by 1 inch / 2.5 cm or more, so that any local reactions can be differentiated (40).

Pentacel and ENGERIX-B (as applicable) should be given in the same thigh. They should not be administered in the same thigh as SP0202 or Prevnar. For details see Operating Guidelines.

Failure to administer vaccines in the designated limb will not constitute a protocol deviation, but should be recorded as a comment in the vaccination form of the eCRF. If the vaccines are not administered in the recommended limb(s), this should be corrected for subsequent injections.

- 11) Keep the subject under observation for 30 minutes and report any reaction / event in the source document.
- 12) Record the date of injection, site of injection, route of administration, as well as the dose number of the vaccine.
- 13) Give the parent / guardian a DC1 to record any injection site and systemic AEs, together with instructions for its completion, including explanations on the definition and use of intensity scales for collection of AEs. Remind parents to carefully report any clinical signs / diagnosis experienced at the same time as the fever episode $> 39.5^{\circ}\text{C} / 103.1^{\circ}\text{F}$.
- 14) Give the parent / guardian a thermometer for rectal temperature measurements, and a ruler to measure the size of any injection site reactions, and go over the instructions for their use.
- 15) Arrange an appointment for V02 ($D60 \pm 14$ days). Remind the parent / guardian to expect a telephone call 8 days after V01 and to bring back the DC1 when they return for V02 at a specified date and time.
- 16) Remind the parent / guardian to notify the site in case of a serious medical event occurs.
- 17) Complete the source document and relevant CRFs for this visit.

Telephone Call 1 (8 [+2] days after Visit 1)

Note: If D8 falls on a weekend or a holiday, the telephone call may be made on the following business day.

- 1) Record relevant information concerning the subject's health status on the telephone contact form. If an SAE occurred, follow the instructions in [Section 10](#) for reporting it.
- 2) Remind the parent / guardian to do the following:
 - Complete the Day 0–7 pages of the DC1
 - Complete the remaining pages of the DC1, and bring them to V02
 - Notify the site in case of an SAE

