Visit 2 (60 [±14] days after Visit 1): Collection of Safety Information and Vaccination

- 1) If the DC1 information from Day 0–7 has not yet been obtained, obtain it at this time by interviewing the parents. Review the pages of the DC1 with the parent / guardian, including any AEs, medications, or therapy that occurred since vaccination.
- 2) Check medications and record reportable ongoing medications.
- 3) Conduct a physical examination, including, but not limited to, examination of the head (ear, nose, and throat), neck, heart, lungs, abdomen, and extremities. If a routine examination had been performed within the past week by a qualified health care provider, it does not need to be repeated unless there were changes in health status, in which case it may be limited to the affected area.
- 4) Take the subject's temperature. If the temperature is $\geq 38.0^{\circ}\text{C}$ / $\geq 100.4^{\circ}\text{F}$, postpone vaccination until the condition is resolved.
- 5) Contact IRT system for vaccine allocation.
- 6) Inject the following study vaccines. Each vaccine should be administered in an assigned location (see Operating Guidelines) and documented appropriately. Refer to [Table 5.3](#) for details on vaccinations and route of administration at V01, V02, and V03.

When multiple vaccines are administered at a single visit, each vaccine should be administered at a different anatomic site. If vaccines are given in the same limb, the injection sites should be separated by 1 inch / 2.5 cm or more, so that any local reactions can be differentiated ([40](#)).

Pentacel and ENGERIX-B (as applicable) should be given in the same thigh. They should not be administered in the same thigh as SP0202 or Prevnar. For details see Operating Guidelines.

Failure to administer vaccines in the designated limb will not constitute a protocol deviation, but should be recorded as a comment in the vaccination form of the eCRF. If the vaccines are not administered in the recommended limb(s), this should be corrected for subsequent injections.

- 7) Keep the subject under observation for 30 minutes and record any adverse reaction in the source document.
- 8) Give the parent / guardian a DC2. Remind parents to carefully report any clinical signs / diagnosis experienced at the same time as the fever episode $> 39.5^{\circ}\text{C} / 103.1^{\circ}\text{F}$.

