- 9) Arrange an appointment for V03 ($D120 \pm 14$ days). Remind the parent / guardian to expect a telephone call 8 days after V02 and to bring back the DC2 when they return for V03 at a specified date and time.
- 10) Remind the parent / guardian to notify the site in case of a serious medical event occurs.
- 11) Complete the source document and the relevant CRFs for this visit.

Telephone Call 2 (8 [+2] days after Visit 2)

Note: If D8 falls on a weekend or a holiday, the telephone call may be made on the following business day.

- 1) Record relevant information concerning the subject's health status on the telephone contact form. If an SAE occurred, follow the instructions in [Section 10](#) for reporting it.
- 2) Remind the parent / guardian to do the following:
 - Complete the Day 0–7 pages of the DC2
 - Complete the remaining pages of the DC2, and bring them to V03
 - Notify the site in case of an SAE

Visit 3 (60 [±14] days after Visit 2): Collection of Safety Information and Vaccination

- 1) If the DC2 information from Day 0–7 has not yet been obtained obtain it at this time by interviewing the parents. Review the pages of the DC2 with the parent / guardian, including any AEs, medications, or therapy that occurred since vaccination.
- 2) Check medications and record reportable ongoing medications.
- 3) Conduct a physical examination, including, but not limited to, examination of the head (ear, nose, and throat), neck, heart, lungs, abdomen, and extremities. If a routine examination had been performed within the past week by a qualified health care provider, it does not need to be repeated unless there were changes in health status, in which case it may be limited to the affected area.
- 4) Take the subject's temperature. If the temperature is $\geq 38.0^{\circ}\text{C} / \geq 100.4^{\circ}\text{F}$, postpone vaccination until the condition is resolved.
- 5) Contact IRT system for vaccine allocation.

- 6) Inject the following study vaccines. Each vaccine should be administered in an assigned location (see Operating Guidelines) and documented appropriately. Refer to [Table 5.3](#) for details on vaccinations and route of administration at V01, V02, and V03.

When multiple vaccines are administered at a single visit, each vaccine should be administered at a different anatomic site. If vaccines are given in the same limb, the injection sites should be separated by 1 inch / 2.5 cm or more, so that any local reactions can be differentiated (40).

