Pentacel and ENGERIX-B (as applicable) should be given in the same thigh. They should not be administered in the same thigh as SP0202 or Prevnar. For details see Operating Guidelines.

Failure to administer vaccines in the designated limb will not constitute a protocol deviation, but should be recorded as a comment in the vaccination form of the eCRF. If the vaccines are not administered in the recommended limb(s), this should be corrected for subsequent injections.

- 7) Keep the subject under observation for 30 minutes and record any adverse reaction in the source document.
- 8) Give the parent / guardian a DC3. Remind parents to carefully report any clinical signs / diagnosis experienced at the same time as the fever episode $> 39.5^{\circ}\text{C} / 103.1^{\circ}\text{F}$.
- 9) Arrange an appointment for V04 (D150 + 14 days). Remind the parent / guardian to expect a telephone call 8 days after V03 and to bring back the DC3 when they return for V04 at a specified date and time.
- 10) Remind the parent / guardian to notify the site in case of a serious medical event occurs.
- 11) Complete the source document and the relevant CRFs for this visit.

Telephone Call 3 (8 [+2] days after Visit 3)

Note: If D8 falls on a weekend or a holiday, the telephone call may be made on the following business day.

- 1) Record relevant information concerning the subject's health status on the telephone contact form. If an SAE occurred, follow the instructions in [Section 10](#) for reporting it.
- 2) Remind the parent / guardian to do the following:
 - Complete the Day 0–7 pages of the DC3
 - Complete the remaining pages of the DC3, and bring them to V04
 - Notify the site in case of an SAE

Visit 4 (30 [+14] days after Visit 3): Collection of Safety Information and Blood Sample

- 1) If the DC3 information from Day 0–7 has not yet been obtained, obtain it at this time by interviewing the parents. Review the pages of the DC3 / eDC3 with the parent / guardian, including any AEs, medications, or therapy that occurred since vaccination.

- 2) Check medications and record reportable ongoing medications. Review temporary contraindications for blood sampling. Ensure the subject has not had any antibiotics within the previous 72 hours (3 days).
- 3) Conduct a physical examination and take subject's temperature if necessary, based on the health status of the subject.

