9.1.1.3.2 Reactogenicity (Solicited Reactions From Day 0 to Day 7 After Each Vaccination)

After each vaccination, subjects parents / guardians will be provided with a DC / eDC, a digital thermometer, and a flexible ruler, and will be instructed how to use them. The following items will be recorded by the subjects in the diary card on the day of vaccination and for the next 7 days (ie., Day 0 through Day 7) until resolution:

- Daily temperature, with the route by which it was taken
- Daily measurement or intensity grade of all other solicited injection site and systemic reactions
- Action taken for each event (eg, medication)

The action(s) taken by the parent or guardian to treat and/or manage any **solicited reactions** will be classified in the CRB using the following list (all applicable items should be checked):

- None
- Medication
- Health care provider contact
- Hospitalized
- Discontinuation of study vaccination

Subjects' parents / guardians will be contacted by telephone 8 days after each vaccination to remind them to record all safety information in the DC / eDC.

If the timing of the telephone call should fall on a weekend or a holiday, the call should be made on the next business day. If contact is not made on the designated day, study staff will continue calling until contact is made. Every telephone attempt and its outcome will be documented in the source document.

Table 9.1 and **Table 9.2** present, respectively, the injection site reactions and systemic reactions that are prelisted in the DC / eDC, and CRB, together with the intensity scales.

Table 9.1: Solicited injection site reactions: terminology, definitions, and intensity scales

CRB term (MedDRA lowest level term [LLT])	Injection site tenderness	Injection site erythema	Injection site swelling
Diary card term	Tenderness	Redness	Swelling
Definition	Pain when the injection site is touched or injected limb mobilized	Presence of a redness including the approximate point of needle entry	Swelling at or near the injection site Swelling or edema is caused by a fluid infiltration in tissue or cavity and, depending on the space available for the fluid to disperse, swelling may be either soft (typically) or firm (less typical) to touch and thus can be best described by looking at the size of the swelling

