13.2 Source Data and Source Documents

“Source data” are the data contained in source documents. Source documents are original documents or certified copies, and include, but are not limited to, diary cards, medical and hospital records, screening logs, informed consent / assent forms, telephone contact logs, and worksheets. The purpose of study source documents is to document the existence of subjects and to substantiate the integrity of the study data collected. Investigators must maintain source documents so that they are accurate, complete, legible, and up to date.

For missing or discrepant data on a diary card, the study coordinator will obtain verbal clarification from the subject, enter the response into the “Investigator’s comment” page of the diary card, and transfer the information to the CRB.

The subject pre-screening log should list all individuals contacted by the Investigators to participate in the study, regardless of the outcome.

The Investigator must print^a any electronic records on an ongoing basis, sign and date them immediately after creation, and keep the printouts on file as source documents that can be verified by the Sponsor or an inspector against the electronic records. Any subsequent changes of an electronic record require the record to be re-printed, dated (with an indication of the date of change), and signed. Such records must also be kept together with the original printed copy.

Good Documentation Practice should be followed by the Investigator and the site staff managing source documents.

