## 4.3 Derived Endpoints: Calculation Methods

### 4.3.1 Safety

#### 4.3.1.1 Solicited Reactions

##### 4.3.1.1.1 Daily Intensity

All daily records for solicited reactions will be derived into daily intensity according to the following classification: None, Grade 1, Grade 2, Grade 3, or Missing (Unknown).

For the derivation of daily intensities, the following sequential steps will be applied:

- 1) Solicited reactions (except Fever/Pyrexia) with an investigator presence recorded as “No” and with all daily records missing (Unknown) then all daily intensities will be derived as None (applicable only for Stage II using DC).
- 2) For non-measurable solicited reactions, daily intensities will correspond to daily records reported in the clinical database. For measurable solicited reactions the daily measurements reported in the clinical database will be converted based upon the intensity scales defined in the protocol; this assumes a reaction that is too large to measure (non-measurable, “NM”) is Grade 3.

Note: The maximum intensity on the ongoing period is derived from the record of the maximum intensity/measurement after the end of the solicited period following the rule described above.

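### Day 0-7 diary entries still absent at the next visit are obtained by parent interview, up to 74 days after Doses 1 and 2, and the analysis plan has no count or sensitivity analysis to check the recall error

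*Protocol*

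**What the plan says.** Protocol 9.1.1.3.2 sets a prospective method: parents record temperature, reaction size and intensity in a diary each day from Day 0 to Day 7. Section 9.1.1.2 makes solicited reactions up to Day 7 a primary safety endpoint after each and any injection.

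Protocol 5.1.4 gives a fallback at the visit after each dose. For infant Dose 1 it reads: "If the DC1 information from Day 0–7 has not yet been obtained, obtain it at this time by interviewing the parents". The same step, with the matching diary card, appears at infant Visit 3 (Dose 2), Visit 4 (Dose 3) and Visit 6 (Dose 4), and at toddler Visit 2. None of these steps limits how long after vaccination recall may be used. The relevant visit headings are "Visit 2 (60 [±14] days after Visit 1): Collection of Safety Information and Vaccination", "Visit 3 (60 [±14] days after Visit 2): Collection of Safety Information and Vaccination" and "Visit 4 (30 [+14] days after Visit 3): Collection of Safety Information and Blood Sample".

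There is an earlier contact. Under 9.1.1.3.2 parents "will be contacted by telephone 8 days after each vaccination to remind them to record all safety information". In 5.1.4 the listed steps for that call are to record health status and to remind the parent to do certain things, the first being "Complete the Day 0–7 pages of the DC1". No step obtains missing Day 0-7 entries.

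On traceability, protocol 13.2 provides that for missing or discrepant diary data "the study coordinator will obtain verbal clarification from the subject". The answer goes on the investigator's comment page of the card and then to the CRB. Section 11.1 has information absent from the diary captured in the source document before electronic entry.

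At analysis, SAP 4.3.1.1.1 states for non-measurable reactions that "daily intensities will correspond to daily records reported in the clinical database", and it converts recorded measurements by the intensity scale. It draws no distinction by how a record was obtained.

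**The concern.** Fever grades turn on 38.5 and 39.5 °C, and redness and swelling grades on 25 and 50 mm (protocol Tables 9.1 and 9.2). If nobody wrote a value down, a parent is unlikely to reconstruct it day by day one or two months later. Short or mild reactions may be forgotten as well.

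Two outputs are exposed. One is the absolute rate of each solicited reaction, which this descriptive trial exists to report. The other is the dose-by-dose profile: the possible delay is longer after Doses 1 and 2 than after Doses 3 and 4, so a change in recall quality could look like a change in reactogenicity. Toddler solicited reactions, which also feed the early safety data review (protocol 5.1.6), have the same fallback at a shorter delay.

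The central difficulty is that a reader of the results could not tell how many entries were recalled, or whether they matter.

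**Working it through.** **Step 1. Delay to interview.** Inputs are the visit intervals and windows in protocol 5.1.4 and the Tables of Study Procedures. Days after the dose = nominal interval with its window. Days after the diary period closes = that figure minus 7.

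| Contact | Interval (days) | Days after dose | Days after Day 7 |
|---|---|---|---|
| Infant Visit 2 (Dose 1) | 60 ± 14 | 46 to 74 | 39 to 67 |
| Infant Visit 3 (Dose 2) | 60 ± 14 | 46 to 74 | 39 to 67 |
| Infant Visit 4 (Dose 3) | 30 + 14 | 30 to 44 | 23 to 37 |
| Infant Visit 6 (Dose 4) | 30 + 14 | 30 to 44 | 23 to 37 |
| Toddler Visit 2 | 30 + 14 | 30 to 44 | 23 to 37 |
| Scheduled call, every dose | 8 + 2 | 8 to 10 | 1 to 3 |

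The call therefore reaches the parent 1 to 3 days after the diary period closes, against as many as 67 days for the visit interview.

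**Step 2. What happens to an interview-derived entry.**

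- Source: marked, on the diary comment page or in the source document (protocol 13.2, 11.1).
- CRB: neither document describes a field for the data source. The CRF itself is not among the documents, so such a field cannot be excluded.
- SAP: daily values in the database are used whatever their origin (4.3.1.1.1). No count, separate table or sensitivity analysis is described.

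Not every interview yields daily values. For the Stage II paper diary, an investigator answer of no, with all daily records missing, becomes None on every day, except for fever (SAP 4.3.1.1.1). The SAP states no matching rule for a yes without daily values. Such a case would stay Missing and leave that endpoint's analysis (SAP 4.3.1.1.3). This asymmetry also tends to lower the reported rate.

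**Step 3. Possible size.** The documents give neither the share of children filled by recall (m) nor the fraction of true reactions that recall captures (s). Both are assumptions. For a true rate p:

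reported rate = p × [(1 − m) + m × s]

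With p = 30%:

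- m = 5%, s = 0.6: 30 × (0.95 + 0.03) = 30 × 0.98 = 29.4%
- m = 10%, s = 0.6: 30 × (0.90 + 0.06) = 30 × 0.96 = 28.8%
- m = 20%, s = 0.4: 30 × (0.80 + 0.08) = 30 × 0.88 = 26.4%

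The shortfall is 0.6 to 3.6 percentage points. For scale, the exact 95% interval for 52 of 175 infants (29.7%) is about 23% to 37%.

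**Step 4. Dose profile under the same kind of assumption.** Take m = 20% at every dose, with s = 0.4 after Doses 1 and 2 and s = 0.6 after Doses 3 and 4. A constant true rate of 30% then reads 26.4% early and 30 × (0.80 + 0.12) = 27.6% late, an apparent rise of 1.2 points due to recall alone.

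**The case against.** The best defence is that the interview is mainly a diary review. The infant paper card stays with the parent and comes back at the next visit, so a card completed faithfully every day is also not yet obtained when the visit starts. Protocol 11.1 describes interviewing parents to collect what the diary contains and to clarify gaps, and the visit step goes straight on to reviewing the pages. This stands. A reader might infer that the step always means recall from two months back. The wording does not support that; true recall is the residual case where nothing was written.

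A reader might also infer that recalled values enter with no mark anywhere. Protocol 11.1 and 13.2 contradict that at source level. Nor does the interview override the SAP 5.3.1 position that missing safety data are generally not replaced: asking the parent is data collection, not imputation.

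The existing call is a safeguard too. It prompts completion soon after Day 7, and staff keep trying until they make contact. But a prompt does not reveal whether the pages were filled.

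Finally, the effect may be small. The shift in the working lies inside the sampling interval, no hypothesis is tested, and groups are randomised and observer-blind (protocol 6.4), so under-recall is probably similar across arms. A reader might infer bias between formulations, or rates shown to be understated. The documents establish neither. What remains is that a systematic error, unlike sampling error, is not reflected in the confidence interval, and the plan provides no way to see it.

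**Conclusion.** The point holds as a gap in collection timing and in analysis. The protocol permits Day 0-7 entries to be obtained by interview up to 74 days after Doses 1 and 2 and up to 44 days after Doses 3 and 4 and the toddler dose, while the listed steps of a call at Day 8 to 10 do not collect them. The source trail exists, but neither document carries it into the analysis data, and the SAP neither counts such entries nor tests their influence.

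The delays follow directly from the visit windows. The effect on the rates does not: the range of about 26% to 29% for a true 30% rests wholly on the assumed m and s, and on recall missing reactions rather than inventing them. If almost every diary is completed on time, the effect is negligible, and a simple count would show it. The change is worth making because it is inexpensive and turns an unknown into something reportable.

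**What to change.** 1. **Protocol 5.1.4, Telephone Calls 1 to 4 (infants) and Call 1 (toddlers).** Add a step: go through Day 0 to Day 7 with the parent and obtain any missing entry during the call.
2. **CRB.** For any Day 0-7 entry first obtained by interview at a later visit, and not from a written diary, record the source and the interview date.
3. **SAP 4.3.1.1.1 and 5.1.1.2.** Keep the main solicited-reaction table as planned. Report the number of such entries by group and dose, and add one sensitivity table of solicited reactions that excludes them.

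Recalled temperatures and sizes should not be forced to Missing in the main analysis. Under SAP 4.3.1.1.3 a child with no non-missing value leaves that endpoint's denominator, so the rule could discard a reported high fever or large reaction only because it was not written down.

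If the calls have already taken place, items 2 and 3 can still be built before database lock from the comment pages and source documents that 13.2 and 11.1 require.

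The cost is a few more minutes per call, one CRB field and one repeat table.
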